## Clinical Study Protocol Synopsis

**Title:** A Prospective, Single-Arm Study Evaluating Crosslinked Hyaluronate Canalicular Gel for the Treatment of Dry Eye Disease in Patients Undergoing Refractive Cataract Surgery

**Principal Investigator:** [name], OD / [name]

**Sponsor Location:** Vance Thompson Vision  
[name]  
[name]

**Study Name:** Crosslinked Hyaluronate Canalicular Gel: A Benefit Study

**Objective:** To determine patient reported outcomes of hyaluronate crosslinked canalicular gel placed in patients undergoing refractive cataract surgery

**Background:** Dry eye disease (DED) is a prevalent condition among patients presenting for cataract surgery, with nearly 50% exhibiting signs of DED, even if asymptomatic. As a result, DED is often undiagnosed and underreported in patients undergoing cataract surgery. This pre-existing condition can be exacerbated by the surgical procedure itself, leading to increased ocular surface irritation, fluctuating vision, and overall discomfort after surgery. Consequently, despite achieving an improvement in vision from the cataract removal, patients may report dissatisfaction due to these persistent DED symptoms, highlighting a critical gap in aligning surgical success with patient-reported outcomes.

The cataract surgery process, involving corneal incisions and abundant use of perioperative medications, can disrupt tear film stability and worsen DED. Therefore, perioperative identification and management of DED is essential to optimize the visual and refractive outcome of the surgery. Addressing ocular surface health prior to surgery contributes to improved accuracy of biometric measurements, which are critical for intraocular lens (IOL) power calculations and achieving desired refractive targets. Proactive management helps stabilize and prepare the ocular surface, potentially reducing postoperative complications and ensuring that patient expectations are more closely met.

Fortunately, the dry eye treatment landscape continues to evolve which enables more individualized care for patients. Recently, a cross-linked hyaluronic acid canalicular gel (Lacrifill®) was introduced, which represents a novel, alternative solution for lacrimal occlusion. This treatment works by occluding the tear drainage system, thereby increasing the retention of natural tears, improving tear film stability, and reducing ocular surface irritation. Proactive use of the canalicular gel could lead to more reliable pre-operative measurements, better visual outcomes, and increased post-operative comfort, which is particularly important for

patients receiving advanced technology IOLs. Improvements in both signs and symptoms of DED have been reported using lacrimal occlusion, suggesting it could play a valuable role in optimizing the cataract surgery experience.

**Study Design:** Prospective, single-site, single-arm study enrolling 60 patients who have elected advanced IOL implantation at the time of cataract surgery and have a diagnosis of dry eye disease. The study will consist of 5 study visits, over a 3-5 month time period. Patients will receive bilateral lacrimal occlusion of crosslinked hyaluronate canalicular gel pre-operatively

The primary endpoint will be the change from baseline to 3- month visit in non-invasive tear break up time (NITBUT) in primary eyes as measured by a non-invasive, automated ocular surface analyzer. Additional endpoints measured will be the change from baseline in the visual analog score and OSDI. The effect of pre-operative lacrimal occlusion on accuracy of preoperative biometry/keratometry measurements will be evaluated as well as residual refractive error at 30 and 90 days post-operative.

**Subject Population:** 60 subjects, who have elected bilateral refractive cataract surgery will be enrolled.

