## Materials and Methods

- Informed consent will be obtained prior to collection of any study specific data.
- Each subjects' demographics, medical and ocular history will be reviewed.
- Inclusion and exclusion criteria will be reviewed for each subject.
- Subjects will be asked to report satisfaction using the visual Analog Score (VAS) and dry eye symptoms using the Ocular Surface Disease Index (OSDI)
- Subjects' monocular and binocular uncorrected distance visual acuity (UDVA) will be obtained on an ETDRS chart at a distance of 4 meters
- A manifest refraction will be performed on each subject.
- Monocular and binocular best corrected distance visual acuity (BCDVA) will be obtained on an ETDRS chart at a distance of 20 feet in photopic lighting conditions.
- Biometry measurements will be obtained.
- Objective tear meniscus height will be measured.
- Objective non-invasive tear break up time will be measured.
- The subjects' eyes will be thoroughly examined at the slit lamp.
- Bilateral canalicular occlusion with cross-linked hyaluronate will be performed prior to cataract surgery
- Patients will undergo standard of care cataract post-operative visit testing and procedures

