**Visit 0 (7 to 45 days prior to surgery):**

- Informed consent will be obtained prior to collection of any study-specific data.
- Potential subjects' demographics, medical and ocular history, and concomitant medications will be reviewed.
- Inclusion and exclusion criteria will be reviewed for each subject.
- Ocular Surface Disease Index (OSDI) will be obtained
- Visual Analog Score will be obtained

- Pre-operative biometry measurements will be obtained
- Non-invasive tear break up time (NITBUT) will be obtained
- Automated tear meniscus (TMH) will be obtained
- Best-corrected distance visual acuity (BCDVA) will be obtained using the ETDRS
- Slit Lamp Exam
- NaFl staining will be measured (NEI grading scale)
- If both eyes qualify for the study, the primary eye will be the eye with the smaller NITBUT. If the NITBUT is the same in both eyes, the primary eye will be the right eye.
- Lacrimal occlusion of the inferior canaliculi of both eyes will be performed

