**Visit 1A/B (operative day[s]):**

- Repeated biometry measurements obtained on each eye
- VAS
- Patients may undergo sequential bilateral surgery per site standard of care
- Adverse events will be collected

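### The VAS and OSDI changes combine gel and cataract surgery in a single arm, and the one VAS reading that could precede surgery is not fixed as such

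*Protocol*

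**What the plan says.** The objective in the Protocol Synopsis is "To determine patient reported outcomes of hyaluronate crosslinked canalicular gel placed in patients undergoing refractive cataract surgery". Under Study Design the trial is described as "Prospective, single-site, single-arm study enrolling 60 patients who have elected advanced IOL implantation at the time of cataract surgery", so there is no comparison group. The primary endpoint is NITBUT. For the patient-reported measures the same section says "Additional endpoints measured will be the change from baseline in the visual analog score and OSDI" and names no follow-up visit. Materials and Methods gives the content of the two instruments: "Subjects will be asked to report satisfaction using the visual Analog Score (VAS) and dry eye symptoms using the Ocular Surface Disease Index (OSDI". It does not say what the satisfaction refers to.

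The baseline is "Visit 0 (7 to 45 days prior to surgery". OSDI and VAS are both collected then, and bilateral gel placement is the last item listed for that visit. The operative-day section covers Visits 1A and 1B under one heading. It lists VAS once, does not list OSDI, and adds that "Patients may undergo sequential bilateral surgery per site standard of care". OSDI and VAS are next collected together at Visits 3, 4 and 5, at 7, 30 and 90 days after surgery.

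**The concern.** Two interventions fall between baseline and the main follow-up: the gel and replacement of the lens by an advanced IOL. With no control arm, a change in VAS or OSDI from Visit 0 to Visits 3 to 5 is the sum of both effects, plus anything else that changes over time. The objective nevertheless speaks of the outcomes of the gel.

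The protocol does provide a post-gel, pre-operative evaluation for biometry and keratometry, with repeat biometry on the operative day. It defines no such evaluation for the patient-reported measures, which are what its objective names. The operative-day VAS could serve, but only if it is taken before the operation and kept apart from a reading made after the first eye has been operated on. The text secures neither. A VAS score collected after surgery cannot be turned into a pre-surgery score by any later analysis.

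**Working it through.** **1. The schedule set out by instrument** (Visit 0 to Visit 5 sections)

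| Visit | Gel placed | Surgery | OSDI | VAS |
|---|---|---|---|---|
| 0 | last item listed | none yet | yes | yes |
| 1A | yes | none yet, if VAS is taken first | no | listed once for 1A/B |
| 1B, if a separate day | yes | first eye done | no | not distinguished from 1A |
| 2 | yes | post-operative | no | no |
| 3, 4, 5 | yes | post-operative | yes | yes |

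OSDI has three follow-up readings, all post-operative. VAS has those three plus the operative-day reading. That reading is the only patient-reported one that can lie after gel and before surgery.

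**2. What the change estimates.** Write the mean change at Visits 3 to 5 as

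D = G + S + T,

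where G is the gel effect, S the surgery effect, and T placebo response, regression to the mean and time. One arm gives one D per instrument and visit, so G cannot be separated from S. For a VAS taken at Visit 1A before surgery, D = G + T: S drops out and T stays.

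**3. The sign of S.** The Background speaks of patients who are dissatisfied "despite achieving an improvement in vision from the cataract removal", and puts the dissatisfaction down to persisting dry eye symptoms. It also says the surgical process can destabilise the tear film and aggravate dry eye. Better vision would push satisfaction up; worse dry eye would push OSDI and satisfaction the wrong way. The documents do not settle the net sign, least of all for OSDI.

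**4. The plan's own figure.** The only power statement is for NITBUT: 60 eyes, 80% power, change of 0.8 s. SD, alpha and sidedness are not given. Taking two-sided 0.05, the implied SD of change is 0.8 × √60 / (1.960 + 0.842) = 6.197 / 2.802 = 2.21 s (2.18 s by the noncentral t). This does not bear on VAS or OSDI, for which no SD, effect or power is stated.

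**5. Illustration of the exposure.** Assumptions, not document figures: one-sample t test of the change, n = 60, two-sided 0.05, G = T = 0, and S expressed in SDs of the change score. The noncentrality is S × √60 = 7.746 × S, with 59 degrees of freedom.

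| S (SD) | Noncentrality | P(significant change) |
|---|---|---|
| 0 | 0 | 0.05 |
| 0.1 | 0.77 | 0.12 |
| 0.2 | 1.55 | 0.33 |
| 0.3 | 2.32 | 0.63 |
| 0.5 | 3.87 | 0.97 |
| 0.8 | 6.20 | >0.99 |

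The same table shows masking. If G = 0.3 SD and S = −0.3 SD, then D = 0 and the probability of a significant change is 0.05, against 0.63 for the gel effect alone. If S = −0.1 SD, then D = 0.2 SD and the probability is 0.33.

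**The case against.** The objective can be read as descriptive: how patients who have the gel and then surgery report they are doing. The rationale includes comfort after surgery, so post-operative readings are on target. The single-arm design is declared in the title, VAS and OSDI are additional endpoints, and the choice of visits for analysis may be in a statistical analysis plan that is not shown. Much of this stands. The post-operative readings should be kept, and leaving the analysis visit unnamed is not in itself an error. What does not follow is that those readings describe the gel. When the VAS is collected on the operative day is also a matter of data collection, which an analysis plan cannot repair afterwards.

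A reader might infer more than the text supports:

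- **That the changes mainly record lens replacement, or that an inert gel would show a large benefit.** No effect sizes are given, and the Background names surgery effects in both directions.
- **That Visit 1A and 1B scores are pooled, or that Visit 1A is left out of the endpoint.** The two visits share a heading, but no rule for combining scores is written, and an endpoint with no visit named does not exclude Visit 1A. The heading also allows a single operative day, in which case there is no separate 1B reading.
- **That the OSDI bias can be stated in points.** The documents give neither the scoring nor an expected surgical change.

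It is also fair to say that the Visit 0 to 1A change does not isolate the gel. It is uncontrolled, it covers a variable 7 to 45 days if the window is counted to the first operation, and satisfaction is a broad question.

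**Conclusion.** The point holds as one of confounding and an unfixed reading. VAS and OSDI changes at Visits 3 to 5 are outcomes of gel plus cataract surgery, with a surgery contribution of unknown size and sign. The case is stronger for VAS, a satisfaction score in patients who have received lenses they chose. For OSDI the bias could as easily hide a gel benefit as create one. The 33% to 97% range rests on assumed surgery-only shifts of 0.2 to 0.5 SD, no gel effect and a simple pre/post test; it shows sensitivity and does not estimate the bias.

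The only patient-reported reading that could exclude surgery is the first operative-day VAS, and the protocol neither times it before surgery nor separates it from Visit 1B. The primary NITBUT sample size is not touched by this point. The change is worth making because these endpoints carry the stated objective and the needed reading is already scheduled.

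**What to change.** 1. In the operative-day section, specify that the Visit 1A VAS is taken before the first operation, and record 1A and 1B as separate readings. Report the Visit 0 to Visit 1A change, without 1B scores, as the pre-surgery patient-reported contrast. State with it that it removes the surgery effect but remains open to placebo response and regression to the mean, and that OSDI has no equivalent reading in the present schedule.
2. In the Objective and Study Design text, describe the VAS and OSDI changes at Visits 3 to 5 as outcomes of gel plus cataract surgery, not of the gel alone.

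The cost is protocol wording and one instruction to site staff, with no added visit, instrument or patient. The downside is that the post-operative patient-reported changes can no longer be presented as the gel's benefit.

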**Visit 4 (30 days post cataract surgery +/- 7 days)**

- OSDI
- VAS
- NITBUT
- TMH
- Manifest refraction
- UCDVA/BCDVA measured by ETDRS
- Slit lamp exam
- Corneal fluorescein staining
- Intraocular pressure measured by standard of care
- Dilated fundus exam
- Adverse events will be collected

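### Can this single-arm study judge the gel's effect on biometry accuracy when no reference for accuracy is stated?

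*Protocol*

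**What the plan says.** The Study Design paragraph of the Protocol synopsis names change in non-invasive tear break-up time as the primary endpoint. It then states, among the additional evaluations, that "The effect of pre-operative lacrimal occlusion on accuracy of preoperative biometry/keratometry measurements will be evaluated", and continues "as well as residual refractive error at 30 and 90 days post-operative". The Background gives the motive: a healthier ocular surface contributes to "improved accuracy of biometric measurements, which are critical for intraocular lens (IOL) power calculations and achieving desired refractive targets".

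The visit schedule supplies these data:

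- Visit 0, timed "7 to 45 days prior to surgery": "Pre-operative biometry measurements will be obtained". The last item of the same visit is "Lacrimal occlusion of the inferior canaliculi of both eyes will be performed".
- Visit 1A/B, operative day(s): "Repeated biometry measurements obtained on each eye".
- Visits 4 and 5 (30 and 90 days): "Manifest refraction" is listed at each.

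The Protocol does not say what accuracy is measured against, which biometry set selects the lens, or how the two sets are compared. The Data Analysis and Data Monitoring section says only that all primary and secondary endpoints will be analysed, and that fellow eyes and all eyes enter secondary analyses.

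**The concern.** The sentence places an effect of the gel on measurement accuracy next to a postoperative outcome that cannot carry such an effect. There is no control arm and no untreated fellow eye, and each eye receives one lens and so has one refractive result. If residual error turned out low, a reader might credit the gel, although the design offers no comparison.

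The two biometry sets do offer a before/after comparison. A difference in keratometry between them, however, shows only that the readings moved, not that they moved towards the truth. Accuracy in the sense of the Background (lens power and refractive target) needs a refractive reference, and none is tied to the biometry pair. At stake is a published claim of better biometry accuracy that the data, analysed naively, would not support.

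**Working it through.** The plan states no figure for this endpoint, so there is none to reproduce. The sample size of 60 was set for tear break-up time (80% power, 0.8 s).

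**Step 1: what residual error contains.** Let e be the error common to both predictions (formula, lens position, refraction; SD s), x0 the biometry error at Visit 0 (SD b0) and x1 the biometry error on the operative day (SD b1), all independent, normal and centred at zero. If Visit 0 biometry selects the lens, residual error is e + x0, and its mean absolute value is √(2/π)·√(s² + b0²). This does not contain b1. If operative-day biometry selects the lens, b1 replaces b0 and the pre-gel error drops out. In neither case does residual error compare the two sets.

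The documents give no dioptre SD, so these are assumptions: s = 0.30 or 0.45 D, b0 = 0.20 to 0.40 D. For selection at Visit 0:

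- smallest: 0.798 × √(0.30² + 0.20²) = 0.29 D
- largest: 0.798 × √(0.45² + 0.40²) = 0.48 D

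Each value is the same whether or not the gel improved the later biometry. This part of the concern is correct.

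**Step 2: whether the scheduled data can answer the question.** Predict the refraction of the implanted lens from each biometry set with the same formula, and score both against the same manifest refraction. The paired difference is d = |e + x0| − |e + x1|, with mean √(2/π)·[√(s² + b0²) − √(s² + b1²)]. It is zero when b1 = b0 and positive when the operative-day set is better. Everything this needs from the clinic is scheduled: both biometry sets and the refraction. The lens and formula are surgical-record items.

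**Step 3: how much 60 eyes could show.** SDs of d come from 1,000,000 simulated eyes per scenario. The 95% CI half-width is t(0.975; 59)·SD/√60, and power is from the noncentral t, two-sided 5%.

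| s (D) | b0 (D) | Mean d, b1 = 0.5·b0 | SD of d | CI half-width | Power | Mean d, b1 = 0.8·b0 | Power |
|---|---|---|---|---|---|---|---|
| 0.30 | 0.20 | 0.035 | 0.188 | 0.049 | 30% | 0.016 | 9% |
| 0.30 | 0.30 | 0.071 | 0.262 | 0.068 | 54% | 0.032 | 13% |
| 0.30 | 0.40 | 0.111 | 0.330 | 0.085 | 73% | 0.049 | 17% |
| 0.45 | 0.20 | 0.025 | 0.199 | 0.051 | 16% | 0.012 | 7% |
| 0.45 | 0.30 | 0.053 | 0.282 | 0.073 | 30% | 0.025 | 9% |
| 0.45 | 0.40 | 0.088 | 0.358 | 0.092 | 46% | 0.040 | 12% |

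SD and half-width are for the halving case. The difference detectable with 80% power is 0.368·SD, which is 0.07 to 0.13 D there (0.368 × 0.188 = 0.069; 0.368 × 0.358 = 0.132). No scenario reaches 80% power, even when the gel is assumed to halve biometry error.

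**Step 4: what the text commits to.** Neither the Study Design paragraph nor the Data Analysis section proposes to compare raw keratometry, or to read residual error as a gel effect. The joining words in "as well as residual refractive error at 30 and 90 days post-operative" naturally make residual error a separate outcome, which is descriptive in a single arm.

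**The case for a change.** The strongest case for a change is that the lack of a contrast in residual error is a matter of design, which no SAP can repair. In addition, the back-calculation needs lens model, lens power, formula and the biometry set used for selection, and the visit lists name none of these. Lens model and power should be recoverable from surgical records. The formula and the set used might not be unless someone captures them on purpose. Capture would add no visit or measurement, only about four data fields per eye, and without it a low residual error or a keratometry shift could be presented as better accuracy.

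The design point stands, but it counts against a claim the Protocol does not make. The record-keeping point stands as sensible practice. It does not show an error, because derivation rules and the data they need are often set out in an SAP or case report form, and neither is at hand. It is also too strong to say that only a refractive reference will do. The source that the Background cites for this point is, by its title, about the repeatability of keratometry, and the Study Design text leading up to the endpoint speaks of more reliable measurements, so accuracy may be meant loosely.

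The paired analysis has limits of its own. The two biometry sets lie 7 to 45 days apart without a control, so time, repeat-measurement variation and regression to the mean (entry requires a low tear break-up time) are mixed with the gel. The reference refraction is also taken after occlusion. If the gel still alters the surface then, the reference may favour the operative-day set.

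**Conclusion.** No change to the plan is needed. It is right that residual refractive error in this single arm is descriptive, and that a bare shift in biometry is not evidence of accuracy. But the Protocol asserts neither, and it schedules the data for a proper paired comparison. An analyst in cataract surgery would ordinarily fill the gap with prediction error against the postoperative refraction, reported as a within-eye difference with a confidence interval and described as a change after occlusion.

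The size is modest. This is an additional endpoint, and the primary analysis is untouched. Under the assumed SDs the paired difference is 0.025 to 0.11 D with a halving of biometry error (power 16% to 73%) and 0.012 to 0.049 D with a reduction of one fifth (about 7% to 17%). These figures rest wholly on assumed dioptre SDs. The conclusion that residual error holds no gel contrast does not depend on them; it follows from the design.

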## Materials and Methods

- Informed consent will be obtained prior to collection of any study specific data.
- Each subjects' demographics, medical and ocular history will be reviewed.
- Inclusion and exclusion criteria will be reviewed for each subject.
- Subjects will be asked to report satisfaction using the visual Analog Score (VAS) and dry eye symptoms using the Ocular Surface Disease Index (OSDI)
- Subjects' monocular and binocular uncorrected distance visual acuity (UDVA) will be obtained on an ETDRS chart at a distance of 4 meters
- A manifest refraction will be performed on each subject.
- Monocular and binocular best corrected distance visual acuity (BCDVA) will be obtained on an ETDRS chart at a distance of 20 feet in photopic lighting conditions.
- Biometry measurements will be obtained.
- Objective tear meniscus height will be measured.
- Objective non-invasive tear break up time will be measured.
- The subjects' eyes will be thoroughly examined at the slit lamp.
- Bilateral canalicular occlusion with cross-linked hyaluronate will be performed prior to cataract surgery
- Patients will undergo standard of care cataract post-operative visit testing and procedures

